4.2.3 Randomized set (RND)

The RND set will consist of all patients in the ENR set who are randomized to the study, regardless of whether they receive the IMP or not. The RND population will be used for the primary analysis of the study (including the Analysis of primary endpoint as described in Section Analysis of primary endpoint7.1 and Table 2).

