4.13 Software

All statistical analyses and data processing will be performed using Statistical Analysis Systems (SAS[®]) Software (release 9.4 or later).

5. Evaluation of Demographic and Baseline Characteristics

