7.1 Analysis of primary endpoint

7.1.1 Analysis details

7.1.1.1 Change in OI from baseline to day 7 of treatment

Summary statistics will be provided for the variable and by subgroups defined in section 4.5. For the estimand definition, please refer to section 4.4.1, while for the derivation of the endpoint please refer to section 11.1.1. Summary statistics will include imputed values at Day 7 for patients who die or are extubated, as defined in section 11.1.1.

The change in OI from baseline will be analyzed by means of an ANOVA adjusting by pre-defined factors (treatment, baseline value of the variable, gender, age class (<65, >=65 years) as fixed effect and site as random effect). In the case baseline value for OI is missing, data will be imputed as described below.

If convergence is not reached or the Estimated G-matrix is not positive definite in at least one of the models after imputation, the random effect will be dropped.

Check of the normality assumption will be performed on change from baseline data, before applying imputation process. As per section 4.1, Normality checks (based on visual inspection and statistical tests) are to be performed on observed data and – in case normality on observed data is not met – also on logarithmic scale. When performing normality checks on logarithmic scale, the checks will be performed on the logarithm of the change from baseline, derived as $\log(\text{OI at day 7}) - \log(\text{OI at baseline})$.

If assumption of normality is not confirmed (see section 4.1) analysis on original scale will be kept. An additional supplementary analysis on log-transformed data (on observed data i.e., not on change from baseline) will also be performed (see section 7.1.3.4).

In case of missing baseline OI, a MI approach will be implemented to impute it.

A MI regression model based on Markov Chain Monte Carlo (MCMC) will be created by including treatment, gender, age class (<65, >=65 years), baseline OI and Day 1 OI as covariates. A thousand data sets will be generated. The random seed number will be **CCI**. Details are provided below.

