For the imputation of Day 7 missing data, rules described in section 0 will be applied, and following the estimand definition, for missingness due to treatment discontinuation or any other reason (whichever the reason), MI-RD regression model will be created by including treatment, OI baseline value (imputed as described in this section), gender and age class (<65, >=65 years) as covariates (further details about the MI process are described below).

If there are not enough retrieved dropouts for convergence of MI-RD regression model, the Copy Reference approach will be used using OI baseline value, gender and age class (<65, >=65 years) as

Standard/Forms/Template				
Title		Statistical Analysis Plan Template		
Code		Version	Effective Date	Page
PPD		01	29 Aug 2022	43 of 78

covariates. Imputation of values in the two treatment arms will be done using the non-missing values from all the patients in the control group. The final decision on the use of the MI-RD vs Copy-Reference will be done at the time of the analysis and reported in the CSR.

Whether for MI-RD or Copy-Reference approach, the adjusted estimated changes from baseline for each treatment arm together with the corresponding 95% confidence intervals will be shown. The difference between Reparin and placebo in the change from baseline at Day 7 will be displayed together with the corresponding two-sided 90% confidence interval (in order to reflect the one-sided 95% confidence intervals). One-sided p-value (alpha=0.05 one-sided) will also be displayed for descriptive purpose.

MI process will be implemented as follows:

STEP1: Run MI for OI baseline missing data on 1000 imputations using:

CCI

Use numeric variable in the MCMC model.

At the blinded DRM, a discussion on the pattern of missingness will be held and it will be evaluated if data show a monotone pattern. If it will be evaluated that no monotone pattern is there, the statement “impute=monotone” will be deleted from the SAS code.

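### If the missing-data pattern is found monotone, the SAP keeps the one option under which STEP 1 fills no missing baseline OI, and no later visible step fills it

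*SAP*

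**What the plan says.** SAP 7.1.1.1 states the intent for the OI co-primary directly: "In case of missing baseline OI, a MI approach will be implemented to impute it". The method follows: "A MI regression model based on Markov Chain Monte Carlo (MCMC) will be created", with treatment, gender, age class, "baseline OI and Day 1 OI as covariates". The first step of the process is introduced as "STEP1: Run MI for OI baseline missing data on 1000 imputations using" code that is blacked out in the public version.

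The text after the redaction shows that the code contains `impute=monotone` and gives the rule for keeping it. At the blinded data review, "it will be evaluated if data show a monotone pattern". The rule is then: "If it will be evaluated that no monotone pattern is there, the statement “impute=monotone” will be deleted from the SAS code". The option is removed if the pattern is not monotone and stays if it is.

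STEP 2 imputes Day 7 OI with baseline OI as a covariate. STEP 3 derives the change from baseline. STEP 4 fits the ANOVA, in which baseline OI is a fixed effect. On the analysis set, SAP 4.2.3 says: "The RND population will be used for the primary analysis of the study". SAP 4.11 records that this set was adopted at a regulatory authority's request. On software, SAP 4.13 says: "All statistical analyses and data processing will be performed using Statistical Analysis Systems".

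**The concern.** The rule looks inverted. In the MCMC statement of PROC MI, `impute=monotone` is a partial imputation. It fills just enough cells to turn a non-monotone pattern into a monotone one, so that a second, monotone method can fill the rest. When the pattern is already monotone there is nothing for it to do. The SAP keeps the option in that situation and deletes it in the situation for which it was designed.

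Baseline OI enters the OI analysis three times: as a covariate for the Day 7 imputation, in the change score, and as a covariate in the ANOVA. A patient whose baseline stays missing has no change score and no covariate value, and a mixed-model fit leaves that patient out. What is at stake is whether the OI co-primary covers all randomized patients, as the SAP intends, or silently becomes complete-case on baseline OI.

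**Working it through.** **Inputs.** The engine, model variables and option rule are in SAP 7.1.1.1. The use of SAS is in SAP 4.13. The meaning of the option is standard method knowledge and is not stated in the documents.

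**Step 1: which cells the option fills.** Treatment, gender and age class are taken as complete and listed first. A missing cell is filled only if a later variable in the list is observed for the same patient. The variable order is not visible, so both orders of the OI variables are shown.

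| Order | Patterns present | Monotone? | Option under the SAP | Baseline OI filled |
|---|---|---|---|---|
| Baseline, Day 1 | complete; Day 1 missing; both missing | yes | kept | none |
| Baseline, Day 1 | complete; baseline missing with Day 1 observed; both missing | no | deleted | all, by full MCMC |
| Day 1, baseline | complete; baseline missing with Day 1 observed; both missing | yes | kept | none |

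In either order, if the pattern is monotone in the order used, the option stays and 0 baseline cells are filled. In the second row the option alone would have filled the baseline of patients with Day 1 observed, but there the SAP deletes it and full imputation does the work.

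**Step 2: can it be triggered?** It needs at least one missing baseline OI and a finding of monotone.
- SAP 11.1.1 sets baseline OI to missing when no OI is available before the first dose on Day 1 or from the previous day.
- SAP 3.2.1 and 3.2.2 limit Day 1 to about 12 hours after the first dose, and count a pre-dose Day 1 measurement towards baseline only. Day 1 OI may therefore be missing too.
- In time order, the pattern is monotone if every patient without baseline OI also lacks Day 1 OI.

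**Step 3: is it repaired later?** Not in the visible text. STEP 2 targets Day 7 OI, and STEPS 3 and 4 use baseline OI as it stands. A patient with an observed Day 7 OI, or one assigned for death or extubation, has no described route to a baseline value.

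**Step 4: which runs are affected?** The MAR sensitivity analysis (7.1.2.1) reuses the same baseline values. The FAS and per-protocol repeats (7.1.3.2, 7.1.3.3) rerun the same procedure. VFD uses no baseline value.

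**Step 5: precision.** The plan's own figure is 46.5% of SD 11.5: 0.465 × 11.5 = 5.35 points. The documents do not give the number of missing baselines, so 2, 4 and 6 of 66 are assumptions. With equal arms, margin = t(0.95, n − 2) × √(4/n) × 11.5:

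| Patients lost | n | Margin (points) |
|---|---|---|
| 0 | 66 | 4.73 |
| 2 | 64 | 4.80 |
| 4 | 62 | 4.88 |
| 6 | 60 | 4.96 |

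For example, at n = 60 the multiplier is 0.4316, and 0.4316 × 11.5 = 4.96. The first row treats imputed patients as fully observed, so it slightly flatters imputation. Every row is below 5.35.

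**The case against.** The strongest reply is that the code cannot be seen. The STEP 1 code is redacted, and the SAS code appendix listed in the SAP's contents is not in the available text. MCMC with `impute=monotone` followed by a monotone regression statement is a common workflow and would fill the remaining cells. This stands as a limit: a follow-on statement cannot be excluded. It does not remove the point, because the written process describes none.

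Second, the fault is conditional. In time order, one patient with baseline missing and Day 1 observed makes the pattern non-monotone. The option is then deleted and the imputation works as intended. If monotonicity were assessed in a different order from the one coded, some baselines could also be filled. Both points stand.

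Third, missing baselines should be few. Blood gases and mean airway pressure are scheduled before the first dose, PaO2/FIO2 is an entry criterion, and SAP 11.1.1 allows matching within 12 hours and use of the previous day. This is fair.

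Fourth, the stakes are moderate. No hypotheses are specified, p-values are descriptive, the pattern is reviewed blind, and a complete-case analysis is already planned. This bears on how much the fault matters, not on whether the rule is right.

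A reader might go further and infer that every patient with missing baseline OI is certain to be lost from all 1000 data sets, or that the loss favours one arm. The documents support neither. A patient who lacks both baseline and Day 7 OI might receive a baseline value in STEP 2, or STEP 2 might stop with an error; the SAP covers neither case. And baseline OI is measured before the first dose in a double-blind trial, so excluding treated patients for a missing baseline has no evident direction.

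**Conclusion.** The point holds in conditional form. If at least one baseline OI is missing and the pattern is already monotone in the variable order used, the rule as written leaves baseline OI unimputed in STEP 1, and no visible step makes it good. Patients with an observed or assigned Day 7 OI but no baseline would drop out of the OI co-primary on the Randomized set and out of the MAR run; the FAS and per-protocol repeats carry the same fault. That contradicts the stated intent to impute missing baseline OI and to analyse all randomized patients.

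The conclusion rests on the standard meaning of the SAS option and on there being no follow-on statement in the redacted code. The number of patients is unknown. The loss of precision is probably small: 6 lost from 66 leaves the planned 60 evaluable, within the 10% allowance, at 4.96 points against the planned 5.35. No bias is shown. The harm is an unplanned departure from the all-randomized analysis that could pass unnoticed.

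**What to change.** Delete `impute=monotone` in every case, so that STEP 1 does full-data MCMC imputation whatever the pattern. Alternatively, when the pattern is monotone, replace the MCMC step with a monotone regression step that imputes baseline OI. Rewrite the sentence on the blinded-review decision to match.

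Add a check that no baseline OI is missing in any of the 1000 data sets before STEP 2 begins, and repeat it in the FAS and per-protocol runs. The MAR run inherits the corrected baselines.

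The cost is one SAS option, one SAP sentence and a simple count of missing values. No unblinding is needed and the estimand does not change. If the redacted code already contains a follow-on imputation statement, saying so in the SAP text would settle the matter.

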7.1.2 Sensitivity analyses

Standard/Forms/Template				
Title		Statistical Analysis Plan Template		
Code		Version	Effective Date	Page
PPD		01	29 Aug 2022	45 of 78

Sensitivity analyses are defined to assess the robustness of results on the two primary endpoints versus assumptions used in the statistical model for the main estimator.

7.1.2.1 Missing at Random assumption

The comparison between treatment and control will be performed under MAR conditions.

Oxygenation Index

The following step will be followed for the missing data imputation.

STEP 1: Imputation of baseline value: the same imputed baseline values for the main analysis will be used.

STEP 2: Day 7 missing data will be imputed by means of MI under Missing at Random (MAR) assumption instead of MNAR. The random seed number will be **CCI** MI will be implemented as follows. All missing primary endpoint data (due to treatment discontinuation, study discontinuation, or any other reason, whichever the reason) will be imputed using the datasets created in step 1. MI regression model will include treatment, OI baseline value (as described in step 1), gender and age class (<65, >=65 years) as covariates. According to MAR approach, all patients with non-missing values will be used to inform the MI regression model.

STEP 3: Derive change from baseline (using imputed/non imputed data).

STEP 4: Each of the 1000 datasets with observed and imputed data will be analyzed using the ANOVA model.

STEP 5: Rubin's rule will be used for combining results to draw inference.

The adjusted estimated changes from baseline for each treatment arm together with the corresponding 95% confidence intervals will be shown. The difference between Reparixin and placebo at Day 7 will be displayed together with the corresponding two-sided 90% confidence interval (in order to reflect the one-sided 95% confidence intervals). One-sided p-value (alpha=0.05 one-sided) will also be displayed for descriptive purposes.

Ventilatory-free days

The following step will be followed for the missing data imputation.

STEP 1: Missing data at Day 28 will be imputed using the MI regression model specified in section 7.1.1.2 under the MAR conditions (according to MAR approach, all patients with non-missing values

Standard/Forms/Template				
Title		Statistical Analysis Plan Template		
Code		Version	Effective Date	Page
PPD		01	29 Aug 2022	46 of 78

will be used to inform the MI regression model). A total of 1000 datasets will be created. The random seed number will be **CCI**. These datasets will be used in step #2.

STEP 2: Each of the 1000 datasets with observed and imputed data will be analyzed using the ANOVA model. Rubin's rule will be used for combining results to draw inference.

The difference between Reparixin and placebo at Day 28 will be displayed together with the corresponding two-sided 90% confidence interval (in order to reflect the one-sided 95% confidence intervals). One-sided p-value (alpha=0.05 one-sided) will also be displayed for descriptive purpose.

7.1.3 Supplementary analyses

The following supplementary analyses will be performed for the two primary endpoints.

7.1.3.1 Complete cases

The analysis of the two primary endpoints will be performed on RND set by fitting the ANOVA models described in section 7.1.1.1 on complete cases only i.e., without considering patients with missing primary endpoints, and without implementing any MI.

7.1.3.2 Full Analysis Set

The analysis of the two primary endpoints described in section 7.1.1.1 will be entirely (including MI on baseline and MI-RD on Day 7 data) reproduced on the FAS set instead of RND. For the analysis on the FAS set, the same seeds used for the analysis on RND set will be used. If FAS population will be the same of RND population, the analysis will not be replicated.

7.1.3.3 Per-protocol

The analysis of the two primary endpoints described in section 7.1.1.1 will be entirely (including MI on baseline for OI and MI-RD on Day 7 data for OI and Day 28 data for VFD) reproduced on the PP set instead of RND.

For imputation of baseline OI the random seed number will be **CCI**.

For imputation of OI at day7 and VFD at Day 28 the random seed number will be **CCI**.

In the case where in the PP set there are not enough retrieved dropouts (RD) for convergence of MI-RD regression model or there are any convergence issues that prevent the use of RD approach, the Copy Reference (CR) approach will be used, and a new sensitivity analysis will be implemented using CR also in the Randomized Set (this will ensure comparability of estimates in PP and RND set).

Due to the low sample size in the PP population, in case of convergence issues in the final analysis, age covariate will be removed from the imputation models as well as from the ANOVA model.

Standard/Forms/Template				
Title		Statistical Analysis Plan Template		
Code		Version	Effective Date	Page
PPD		01	29 Aug 2022	47 of 78

In summary the following process will be followed:

1. Run the model using Retrieved Drop-Out (RD) approach (using all covariates).
 - a) If it converges ok, stop.
 - b) If it doesn't converge, follow the next steps.
2. Run the model using Copy Reference (CR) approach (using all covariates).
 - a) If it converges ok, stop here and add a new sensitivity on RND set, i.e., run a model using Copy Reference (CR) approach (using all covariates) on the Randomized Set.
 - b) If it doesn't converge, follow the next steps.
3. Run the model using Copy Reference (CR) approach by deleting age from covariates.
4. Run a new sensitivity on RND set, i.e., run a model using Copy Reference (CR) approach by deleting age from covariates on the Randomized Set

7.1.3.4 Log-transformed scale

As described in section 7.1.1, in the case the assumption of normality on the primary variables is not met, the primary endpoints will be analyzed also using the log-transformed scale.

For the analysis on the log-transformed data, log-transformation will be applied before the multiple imputation step.

For the analysis of VFD at Day 28, before the log-transformation, a +0.5 will be added to the original scale values.

7.1.3.5 Additional clinically relevant adjustment(s)

The analysis of the two primary endpoints described in section 7.1.1 will be entirely reproduced after updating the regression model used for the analysis with further clinically relevant variables that may result imbalanced at baseline (for example specific comorbidities). This decision will be taken at the BDRM (keeping the study team blinded) or after the database lock (in this case the analyses will be considered as ad-hoc).

The following supplementary analysis will be performed only for the primary endpoint referred to change in OI from baseline to day 7.

7.1.3.6 Change in OI from baseline to Day 7 without imputing death and extubation.

This analysis will be performed only on the subset of complete cases only (i.e., without considering patients with missing endpoint) that reached Day 7 still intubated (imputed values of patients who died or were extubated before or at Day 7 with no OI at Day 7 will be classified as missing). Value and change in OI from baseline to Day 7 will be analyzed by means of descriptive statistics as a continuous variable. Comparison between treatments will be performed by means of two-sample t-test and, if assumptions of normality is not confirmed, two-sample Mann-Whitney U test (alpha=0.05 one-sided).

Standard/Forms/Template				
Title		Statistical Analysis Plan Template		
Code		Version	Effective Date	Page
PPD		01	29 Aug 2022	48 of 78

7.2 Analysis of secondary efficacy endpoints

7.2.1 Analysis details

Independently of results on primary, all secondary endpoints (Section 0) will be analyzed and compared by treatment by means of descriptive statistics and by appropriate parametric tests depending on the nature of the variable and its distribution. No multiplicity correction is required. Statistical tests for continuous variables will be performed only for the change from baseline.

The assumption of normality requested by parametric statistical tests, will be checked as described in section 4.1, and in case such assumptions are not met, also non-parametric counterpart tests will be performed. Change from baseline value (for continuous variables) and shift tables versus baseline (for categorical variables) may also be summarized for all post-baseline visits, as described in the following sections. Alpha level to be used for secondary endpoints is 0.05 two-sided.

7.2.1.1 Change in OI from baseline to Day 4

Value and change in OI from baseline to Day 4 will be analyzed by means of descriptive statistics as a continuous variable. Comparison between treatments will be performed by means of two-sample t-test and, if assumptions of normality is not confirmed, two-sample Mann-Whitney U test.

Change from baseline to Day 4 is derived similarly to change from baseline to day 7: details on derivation are provided in section 11.1.1.

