3.5.2 Secondary efficacy endpoints

The following secondary endpoints will be considered.

- Change in OI from baseline to day 4 [study day: date/time]

Standard/Forms/Template				
Title		Statistical Analysis Plan Template		
Code		Version	Effective Date	Page
PPD		01	29 Aug 2022	22 of 78

- Acute lung injury score [composite of PaO₂/FIO₂ ratio, PEEP, lung compliance (plateau airway pressure minus PEEP/TV) and extent of pulmonary infiltrates] at 2, 3, 7, 14 days (if still intubated) [by visit and date/time]
- SOFA scores at 2, 3, 7, 14 days (if still intubated) [study day: date/time]
- Ventilatory ratio at 2, 3, 7, 14 days (if still intubated) [study day: date/time]
- Incidence of ECMO at day 14 [study day: date]
- Use of vasoactive medications at day 14 [study day: date/time]
- Change from baseline of CXR assessment of pulmonary edema by “radiographic assessment of lung edema” (RALE) score at 2, 3, 7, 14 days [by visit]
- Percentage of patients achieving pressure support ventilation equal to 5 cmH₂O with PEEP equal to 5 cmH₂O for 2 hours (measure of weaning) by day 28 and hospital discharge [study day: date]
- ICU-free days by day 28 and hospital discharge [study day: date]
- Hospital-free days by day 28 [study day: date]
- Incidence of tracheostomies by day 28 and hospital discharge [by visit]
- Incidence of LTAC facility by day 28 and hospital discharge [by visit]
- All-cause mortality by day 28 [study day: date]
- Hospital discharge by day 28 [study day: date]
- All-cause mortality by day 60 [study day: date]
- Change from baseline to day 3, 7 and 14 in plasma levels of IL-6, IL-8, PAI-1, Plasma TNFr-1, ICAM-1, RAGE [by visit]

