STEP 2: A MI-RD for Day 7 missing data will be performed on the output datasets created in step 1 (with “nimpute=1”). A thousand datasets will be generated. The random seed number will be CCI. Missing OI data at Day 7 will be imputed using the specified MI regression model. MI regression model will include treatment, OI baseline value (as described in step 1), gender and age class (<65, >=65 years) as covariates. According to MI-RD approach, only non-missing values from retrieve dropouts will be used to inform the MI regression model.

STEP 3: Derive change from baseline (using imputed/non imputed data).

STEP 4: Each of the 1000 datasets with observed and imputed data will be analyzed using the ANOVA model.

STEP 5: Rubin’s rule will be used for combining results to draw inference.

Standard/Forms/Template				
Title		Statistical Analysis Plan Template		
Code		Version	Effective Date	Page
PPD		01	29 Aug 2022	44 of 78

7.1.1.2 VFD at day 28

Summary statistics will be provided for the variable and by subgroups defined in section 4.5. For the estimand definition, please refer to section 4.4.1, while for the derivation of the endpoint please refer to section 11.1.1.

VFD at day 28 will be analysed using an ANOVA model as described in section 7.1.1.1 (considering as covariates: treatment, gender and age class (<65, >=65 years)).

If convergence is not reached or the Estimated G-matrix is not positive definite in at least one of the models after imputation, the random effect will be dropped.

Check of the normality assumption will be performed on the observed data, before applying imputation process.

If assumption of normality is not confirmed (see section 4.1) analysis on original scale will be kept. An additional supplementary analysis on log-transformed data will also be performed (see section 7.1.3.4).

For the imputation of ventilatory free days missing data at day 28, rules described in section 0 will be applied, and following the estimand definition, for missingness due to treatment discontinuation or any other reason (whichever the reason), MI regression model will include treatment, gender and age class (<65, >=65 years) as covariates. A thousand data sets will be generated. The random seed number will be **CCI**. MI will be implemented in the following steps:

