7.2.1.2 Acute lung injury score

Rules for derivation of Acute lung injury score are reported in section 11.1.

Value and change from baseline in Acute lung injury score will be analyzed at Day 2, Day 3, Day 7, Day 14 (if still intubated) timepoints by means of descriptive statistics as a continuous variable. Comparison between treatments will be performed by means of two-sample t-test and, if assumption of normality is not confirmed, two-sample Mann-Whitney U test.

Acute lung injury score classes (as defined in section 11.1.1.) will also be summarized as a categorical variable: number and percentage of patients in each class for each timepoint will be presented and a shift table will be provided.

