7.2.1.6 Use of vasoactive medications

Vasoactive medication use will be defined as described in Section 11.1.

The proportion of patients with at least one vasoactive medication by Day 14 (as defined in section 11.1.1) will be compared by Fisher's exact test or Chi-squared test, depending on data distribution.

7.2.1.7 CXR assessment of pulmonary edema by “radiographic assessment of lung edema” (RALE) score

Value and change from baseline in RALE score will be analyzed at Day 2, Day 3, Day 7, Day 14 (if still intubated) timepoints by means of descriptive statistics as a continuous variable. Comparison between treatments will be performed by means of two-sample t-test and, if assumptions of normality is not confirmed, two-sample Mann-Whitney U test.

7.2.1.8 Percentage of patients achieving pressure support ventilation equal to 5 cmH₂O with PEEP equal to 5 cmH₂O for 2 hours (measure of weaning) by day 28 and at hospital discharge

The proportion of patients achieving pressure support ventilation equal to 5 cmH₂O with PEEP equal to 5 cmH₂O for 2 hours (measure of weaning) by Day 28 and at hospital discharge will be compared by Fisher's exact test or Chi-square's test, depending on data distribution.

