Retrieved drop-out flag for ventilatory free days at day 28	
For "VFD at Day 28" the retrieved dropouts are the patients that discontinued the study treatment (treatment completers/discontinuers are defined above in this table under "Treatment completed/discontinued") and have the endpoint evaluable by Day 28 (death on the day of the treatment discontinuation not part of the retrieved dropout):
 
Set to 'Y' if Subject discontinued the treatment prematurely and patient is alive or have date of death after end of treatment, and the endpoint is not missing for this parameter and timepoint.

Standard/Forms/Template				
Title		Statistical Analysis Plan Template		
Code		Version	Effective Date	Page
PPD		01	29 Aug 2022	63 of 78

Parameter	Calculation
Change in oxygenation index (OI) from baseline to day 4 [study day based on Date/time]	
The endpoint is derived similarly to change from baseline at day 7.
 
 - If patient dies before Day 4, or at Day 4 (Day 4 date = Day 1 date + 3, since only date of death -no time- is collected) and OI is missing: OI at day 4 = 90th percentile of the distribution of the primary variable at Day 4. - If patient at Day 4 is extubated* and OI is not evaluable (i.e., if the patient results not intubated* in the time range [First IMP Intake Date/Time +60h, First IMP Intake Date/Time +83h and 59 min]), OI at day 4 = 10th percentile of the distribution of the primary variable at Day 4. - Otherwise, OI is set to missing. 
*intubation/extubation status at day 4: check intubations in "Extubation Summary" CRF form. Use the multiple entries of extubation/re-intubation: if the last record of intubations/extubations prior day 4 is an extubation, and there are no intubations at day 4, it means the subject was extubated on Day 4.

ICU stay up to Day 28 and up to hospital discharge (days)	The information on ICU length of stay is collected under "Other Clinical Event Form" at Day 28 Visit and at Hospital Discharge Visit

Standard/Forms/Template				
Title		Statistical Analysis Plan Template		
Code		Version	Effective Date	Page
PPD		01	29 Aug 2022	64 of 78

Parameter	Calculation

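### The change-score secondaries, Day 4 OI first among them, are compared by an unadjusted t-test on change, which gives up precision that baseline adjustment would usually recover

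*SAP*

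**What the plan says.** SAP 7.2.1 limits the tests: "Statistical tests for continuous variables will be performed only for the change from baseline". SAP 7.2.1.1 then names the method for Day 4 OI: "Comparison between treatments will be performed by means of two-sample t-test and, if assumptions of normality is not confirmed, two-sample Mann-Whitney U test". The same method, with no covariate, is given for acute lung injury score (7.2.1.2), SOFA (7.2.1.3), ventilatory ratio (7.2.1.4), RALE (7.2.1.7) and the six plasma biomarkers (7.2.1.15). Testing is two-sided at 0.05 without multiplicity correction.

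For the Day 7 OI co-primary, SAP 7.1.1.1 fits a model with "treatment, baseline value of the variable, gender, age class (<65, >=65 years) as fixed effect and site as random effect".

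SAP 11.1.1 says that Day 4 OI is derived in a similar way to Day 7. Patients without an OI value because they died receive the 90th percentile. For those extubated, "OI at day 4 = 10th percentile of the distribution of the primary variable at Day 4".

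Some of these endpoints are restricted further, for example: "change from baseline in Acute lung injury score will be analyzed at Day 2, Day 3, Day 7, Day 14 (if still intubated").

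Protocol 9.5.1.2 calls the secondary analyses descriptive, asks for appropriate parametric tests and leaves the details to the SAP. It neither requires nor excludes baseline adjustment.

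**The concern.** A t-test on change fixes the slope of outcome on baseline at 1. ANCOVA estimates that slope. Where the true slope is below 1, subtracting the whole baseline adds noise to the comparison. Day 4 OI shows this most plainly: a patient given a fixed percentile has a change equal to a constant minus his or her own baseline, so that patient's variation in change is entirely baseline variation.

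The same variable, under the same percentile rule, is adjusted for baseline at Day 7 and not at Day 4, and the SAP gives no reason. In a trial of about 60 evaluable patients, what is at stake is how sharply the treatment differences on these secondaries can be estimated.

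**Working it through.** **Inputs.** 60 evaluable patients, 1:1 (SAP 3.3). The baseline-to-follow-up correlation rho and the SD ratio k = SD_post/SD_base are not in the documents. I assume rho = 0.3, 0.5, 0.7 and k = 1 or 1.5. The plan states no precision for the secondaries, so there is no figure of its own to reproduce; the margin in SAP 3.3 is for the two primaries.

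**Step 1, large-sample SE ratio, ANCOVA against change score.**

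SE ratio = sqrt( k²(1 − rho²) / (1 + k² − 2·rho·k) )

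For example, k = 1 and rho = 0.5 gives sqrt(0.75/1) = 0.866.

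| k | rho 0.3 | rho 0.5 | rho 0.7 |
|---|---|---|---|
| 1 | 0.806 | 0.866 | 0.922 |
| 1.5 | 0.933 | 0.982 | 0.999 |

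The ratio is exactly 1 when rho × k = 1 (for example k = 2, rho = 0.5).

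**Step 2, cost of one covariate.** The SE grows on average by sqrt(1 + 1/(N − 4)), and the t quantile loses one degree of freedom.

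- N = 60: sqrt(1 + 1/56) × 2.0025/2.0017 = 1.009
- N = 30: sqrt(1 + 1/26) × 2.0518/2.0484 = 1.021

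**Step 3, ratio of 95% interval widths (step 1 × step 2).**

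| N | k | rho 0.3 | rho 0.5 | rho 0.7 |
|---|---|---|---|---|
| 60 | 1 | 0.814 | 0.874 | 0.930 |
| 60 | 1.5 | 0.942 | 0.991 | 1.008 |
| 30 | 1 | 0.823 | 0.884 | 0.941 |
| 30 | 1.5 | 0.953 | 1.002 | 1.020 |

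Simulation (3,000 trials per setting) agrees to within about 0.001. With 60 patients and equal SDs, the interval is thus about 18%, 12% or 7% narrower. At k = 1.5 it is 6% narrower, 1% narrower or 1% wider.

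**Step 4, Day 4 OI with percentile values (60 patients, equal SDs; rho 0.3 to 0.7).** The result depends on how extubation and death relate to OI, so three simulations are set side by side.

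| Assumption | Ratio | Gain |
|---|---|---|
| 15–30% filled, events unrelated to OI | 0.80 to 0.91 | 9–20% |
| 15% extubated, 8% dead, events linked to baseline OI (SE ratio) | 0.86 to 0.93 | 7–14% |
| Events tied to OI more generally | about 0.74 to 0.87 | 13–26% |

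Together the range is roughly 7% to 25%. At k = 1.5 with unrelated events, the ratios are 0.924 to 1.004.

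**Step 5, illustration in OI points.** SAP 3.3 assumes an SD of 11.5 for OI without saying whether this is the SD of the value or of the change. If it were the SD of the Day 4 change, the two-sided 95% half-width from the t-test would be 2.0017 × sqrt(2/30) × 11.5 = 5.94 points. Multiplying by the first row of step 3 gives 4.84, 5.19 and 5.53 points.

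**The case against.** **A choice, not an error.** The protocol itself separates the tiers: primaries by adjusted regression (9.5.1), secondaries by descriptive statistics and suitable tests (9.5.1.2). A two-sample t-test meets that wording. This stands, and the point is one of efficiency only.

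**Precision is not what the plan promises here.** The precision in SAP 3.3 concerns the two primaries, and 7.2.1 plans no between-group interval for the continuous secondaries. This also stands. It is why the fix asks for an interval as well as a different model.

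**The gain is assumed.** It is. Entry at PaO2/FIO2 of 200 or below may narrow the baseline spread and so affect both rho and k, and at k = 1.5 little remains. The comparison is also with the t-test, not with Mann-Whitney. What survives is the asymmetry: a possible gain of 7% to 18% or more, against a loss of 1% to 2%.

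**The Day 7 and Day 4 models would still differ.** True: gender, age class and site would remain only in the Day 7 model. Own baseline is the covariate that change-scoring already uses, in a fixed and usually suboptimal way.

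**A reader might extend the point to ventilator-free days**, because that co-primary model has no baseline severity covariate: "VFD at day 28 will be analysed using an ANOVA model as described in section 7.1.1.1 (considering as covariates: treatment, gender and age class". The case is too weak. With 30 per arm and SD 8, adding baseline OI runs from 1% wider at zero correlation to 7% narrower at |r| = 0.4, with no gain below |r| of about 0.14. Missing baseline OI has no clean solution there: the imputed values from Step 1 of 7.1.1.1 draw on Day 1 OI, measured after the first dose, and a single mean fill would depart from the multiple imputation used for the OI co-primary.

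**Conclusion.** The point holds as a precision point. Day 4 OI and the other change-score secondaries are compared without the baseline covariate that the SAP uses for Day 7 OI, and nothing else in the documents supplies it: the further adjustment in SAP 7.1.3.5 covers only the primaries and is supplementary.

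With 60 patients, equal SDs and rho of 0.3 to 0.7, the 95% interval would be about 7% to 18% narrower, and for Day 4 OI roughly 7% to 25%. At k = 1.5 it would be between 6% narrower and 1% wider, and the gain vanishes when rho × k is near 1. All of this rests on assumed correlations and SD ratios.

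Two stronger readings are not supported. The unadjusted comparison is not biased, since randomisation makes the t-test valid. Nor would ANCOVA repair the restriction to patients still intubated for lung injury score, SOFA and ventilatory ratio, or for RALE as worded in SAP 7.2.1.7 ("Value and change from baseline in RALE score will be analyzed at Day 2, Day 3, Day 7, Day 14 (if still intubated")). That selection after randomisation is a separate matter.

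**What to change.** In SAP 7.2.1, for each change-score secondary and first for Day 4 OI, replace the t-test by ANCOVA on change with treatment and the endpoint's own baseline. Report the adjusted difference with its two-sided 95% confidence interval, and keep Mann-Whitney as supportive. The treatment estimate is the same whether the outcome is change or the post-baseline value, so the rule that only change is tested can stay.

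A log-scale biomarker analysis would be an addition. Protocol 9.5.1.2 permits transformation, but SAP 4.1 keeps non-normal secondaries on the original scale and would have to be amended too.

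If unblinding has occurred, report the ANCOVA as a labelled additional analysis.

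Cost: no new data, and no patients lost, because a change score already needs a baseline. The programming is one model per endpoint and timepoint: 1 for Day 4 OI, 4 × 4 for the four scores and 6 × 3 for the biomarkers, 35 in all. Each spends one degree of freedom, which at worst widens the interval by about 1% with 60 patients and 2% with 30.
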